LDH:	lactate dehydrogenase
LDL-C:	low density lipoprotein cholesterol
LLN:	lower limit of normal
LLOQ:	lower limit of quantification
LLT:	lower level term
LS:	least square, least square
MD-VAS:	physician global assessment of disease activity- visual analog scale
MedDRA:	Medical Dictionary for Regulatory Activities
NCEP ATPIII:	National Cholesterol Education Program Adult Treatment Panel III
PT:	preferred term
RBC:	red blood cell
SAEs:	serious adverse events
SMQ:	standardized MedDRA query
SOC:	system organ class
TEAE:	treatment-emergent adverse event
ULN:	upper limit of normal
WBC:	white blood cell
WHO-DD:	World Health Organization - Drug Dictionary

1 OVERVIEW AND INVESTIGATIONAL PLAN

This statistical analysis plan (SAP) provides a comprehensive and detailed description of statistical strategy and methodology to be used to analyze the data from sarilumab EFC15160 study in patients with active polymyalgia rheumatica (PMR).

Due to the ongoing pandemic of COVID-19 (the disease caused by the novel coronavirus), the operations of sarilumab (Kevzara®) clinical trial EFC15160 have been significantly disrupted in various countries and sites. Consequently, the screening/recruitment activities for this study have been suspended since March 2020. Due to the protracted recruitment timeline and internal portfolio reprioritization, in July 2020, Sanofi decided not to re-open the screening/recruitment activities and to discontinue the study. This decision is not related to any safety issues arising from the administration of sarilumab.

A total of 118 patients (out of 280 planned patients) have been randomized in the study. Despite the decision to discontinue the study, all patients already recruited will be allowed to continue in the study to complete the 52-week treatment period and the 6 weeks post-treatment follow up per protocol.

1.1 STUDY DESIGN AND RANDOMIZATION

Original study design

This is a multicenter, randomized, double-blind, placebo-controlled 52-week Phase 3 study with a 6-week post-treatment follow-up phase, evaluating the efficacy and safety of sarilumab in patients with active polymyalgia rheumatica (PMR).

Patients with active PMR who meet the entry criteria will be randomized in a 1:1 ratio to either

- Group 1: sarilumab 200 mg every two weeks (q2w) with a 14-week prednisone taper, or
- Group 2: sarilumab matching placebo q2w with a 52-week prednisone taper.

All patients will receive sarilumab 200 mg or its matching placebo for 52 weeks, while the initial dose of prednisone for both groups will be 15 mg/day for the first 2 weeks after randomization (baseline). To ensure the double blinding of the corticosteroid (CS) regimen thereafter, once daily prednisone and/or prednisone matching placebo will be provided according to the protocol defined CS tapering regimen ([Appendix B](#)) as summarized below.

- Group 1: From Week 2 to Week 13, patients will receive gradually decreasing dose levels of prednisone (prednisone or combinations of prednisone and its matching placebo). From Week 14 onwards, patients without flare will receive prednisone matching placebo.
- Group 2: From Week 2 to Week 51, patients will receive gradually decreasing dose levels of prednisone (prednisone or combinations of prednisone and its matching placebo).

During the initial 12 weeks of prednisone taper, treatment for one flare before Week 12 is permitted if it can be successfully treated with a low dose (≤ 5 mg/day) prednisone add-on taper regimen (completed prior to Week 12) and provided that all other sustained remission parameters are met. For patients who experience a disease flare and are in need of rescue therapy (such as CS) as per investigator judgment, during the course of the study, they may continue administration of sarilumab or matching placebo in a double-blinded fashion for the full duration of the 52-week treatment period only if CS are used as rescue therapy. Treatment with non-biological immunosuppressive drugs (such as alkylating agents, hydroxychloroquine, CsA, MMF, AZA, etc.) is not permitted during the study, unless used for the purpose of rescue therapy.

For the management of pre-defined laboratory abnormalities, investigators may temporarily hold the study drug (sarilumab or its matching placebo) and/or permanently reduce the dose of sarilumab (or its matching placebo) to 150 mg q2w in a continuous blinded manner.

There will be a post treatment follow-up visit 6 weeks after the end of treatment visit. All patients who prematurely and permanently discontinue study treatment will be asked to return to the site for study assessments as per protocol until end of study (EOS) evaluation. The last patient last visit will occur when the last patient has completed the 6-week follow up period (EOS). The end of the clinical trial is defined as the last patient's last visit.

Approximately 280 patients are planned to be randomized into 2 treatment groups of 140 patients per group.

Study discontinuation plan

As mentioned in [Section 1](#), due to the protracted recruitment timeline and internal portfolio reprioritization, Sanofi decided to terminate the EFC15160 study in July 2020. All randomized patients continued to complete the study per protocol, and the last patient last visit (EOS) was achieved on May 19, 2021.

1.2 OBJECTIVES

1.2.1 Primary objectives

The primary objective of this study is to evaluate the efficacy of KEVZARA® (sarilumab) in patients with PMR as assessed by the proportion of patients with sustained remission at Week 52 for sarilumab with a 14-week CS tapering regimen as compared to placebo with a 52-week CS tapering regimen (see [Section 2.1.3.1](#) for definition of sustained remission).

1.2.2 Secondary objectives

- To demonstrate the efficacy of sarilumab (14 week taper of CS) compared to placebo (52 week taper of CS) in patients with PMR with regards to:
 - Clinical responses (such as components of sustained remission, disease remission rates, time to first disease flare) over time.

- Cumulative CS (including prednisone) exposure.
- To assess the safety (including immunogenicity) and tolerability of sarilumab in patients with PMR.
- To measure sarilumab concentrations from serum of patients with PMR.
- To assess the effect of sarilumab on reducing glucocorticoid toxicity as measured by the composite glucocorticoid toxicity index (GTI) questionnaire.

1.2.3 Other objectives

- To assess the effect of sarilumab on physician assessment of disease activity as measured by a visual analogue scale (MD-VAS).
- To assess the effect of sarilumab on a variety of patient-reported outcome (PRO) concepts, including fatigue (as measured by FACIT-fatigue scale), health status (as measured by EQ-5D-3L and SF-36v2), physical function (as measured by HAQ-DI, pain (as measured via HAQ-DI by a visual analogue scale [VAS]) and patient assessment of disease activity (as measured via HAQ-DI by a VAS).
- To assess the correlation between the ESR/CRP levels on remission status.
- To characterize the disease activity of PMR patients while on steroid taper or sarilumab treatment in a subset of patients using comprehensive approaches to evaluate circulating immune cell types.
- To characterize the disease activity of PMR patients while on steroid taper or sarilumab treatment by evaluating circulating proteins, genetics and gene expression.

1.3 DETERMINATION OF SAMPLE SIZE

The sample size calculations are based on the primary efficacy variable of sustained remission at Week 52 compared between the sarilumab + 14-week prednisone taper and placebo + 52-week prednisone taper groups. There are no prior controlled study data to establish the placebo + 52-week prednisone taper remission rate in PMR. The hypothesis to be tested on the primary endpoint is that sarilumab + 14-week prednisone taper is superior to placebo + 52-week prednisone taper based on the proportion of patients achieving sustained remission at Week 52. A 25% difference from placebo + 52-week prednisone taper response rate is considered clinically relevant, and the sample size of 140 per group provides at least 90% power to detect such a difference regardless of the placebo + 52-week prednisone taper response rate (i.e., assuming 5% to 50% placebo + 52-week prednisone taper response rates), using a two-sided χ^2 test at a significance level of 0.01. Data from the GiACTA trial in a related population with GCA suggest that such a treatment difference is achievable (1).

The above sample size calculation was performed for the full enrollment (140 per group). The total number of randomized patients is 118 at the time of the premature termination of the study. Randomized patients could continue in the study to complete the 52-week treatment period per protocol.

Based on protocol amendment 2, the alpha level has been changed from 0.01 to 0.05. The power calculations provided in [Table 1](#) below are based on a sample size of 118 and alpha level of 0.05. The sample size of 59 per group provides at least 85% and 95% power to detect a 25% and 30% difference in response rates between sarilumab + 14-week prednisone taper and placebo + 52-week prednisone taper groups respectively, assuming response rates between 5% to 15% in the placebo + 52-week prednisone taper group based on two-sided χ^2 test at a significance level of 0.05.

Table 1: Power calculations based on total sample size of 118 randomized patients

[figure not shown]
Assumed sustained remission rate for placebo+ 52-week prednisone taper	Sample Size per group	Power assuming an absolute 25% between group difference	Power assuming an absolute 30% between group difference
5%	59	95.6%	98.8%
10%	59	91.2%	97.2%
15%	59	86.9%	95.4%

Calculations were made using nQuery Advisor 7.0 based on two-sided χ^2 test at a significance level of 0.05.

1.4 STUDY PLAN

The schedule of the safety, efficacy, pharmacokinetic (PK), and immunogenicity assessments from Section 1.2 of the study protocol is provided in [Appendix A](#). The graphical study design is provided in [Figure 1](#).

Figure 1 – Graphic study design

1.5 MODIFICATIONS TO THE STATISTICAL SECTION OF THE PROTOCOL

In general, the statistical methods remain unchanged by the protocol amendment 02 except for revisions made to sample size and power calculations as listed below:

Amended protocol 02 (19 April 2021):

As a result of the inability to recruit due to the COVID19 pandemic, the study was terminated prematurely resulting in a change in the total expected number of patients from 280 to 118 (Section 1.3).

- Statistical significance level changed from 0.01 to 0.05 due to the change in total expected number of patients.
- Power calculations revised due to the change in total expected sample size to 118, and the change in statistical significance level to 0.05.
- 99% confidence intervals revised to 95% confidence intervals associated with the change in statistical significance level to 0.05.

1.6 STATISTICAL MODIFICATIONS MADE IN THE STATISTICAL ANALYSIS PLAN

Due to the premature termination of the study, a total of 118 patients (42%) of the 280 patients planned were randomized. The randomized patients could continue in the study to complete the treatment period and the 6 weeks post-treatment follow up per protocol. Hence, there are no changes to the efficacy analysis plan per protocol.

The COVID-19 pandemic has also impacted data collection as patients may not be able to visit clinical sites for endpoint assessments. Additional patient level information at visits that were impacted by the pandemic situations were captured for assessments performed in visits that were delayed, not done, partially done on site, or partially done by phone. Major or critical COVID-19 impacted deviations per protocol were also recorded.

To assess the impact of the pandemic on the study, COVID-19 related summaries are added as below.

- a) Patients who permanently discontinue study treatment or study due to COVID-19 reasons will be summarized in patient disposition table
- b) Patient disposition by visit according to trial impact due to COVID-19
- c) Critical or major deviations summary according to COVID-19 impact
- d) Number (%) of patients experiencing at least one treatment-emergent COVID-19 related adverse event by primary SOC and PT

In addition, if > 10% patients are impacted by the COVID-19 pandemic, below summaries/analyses will be generated by COVID-19 impacted population (Yes, No):

- a) Extent of exposure to SC IMP
- b) Treatment compliance for SC IMP

- c) Number (%) of patients with TEAEs by primary SOC and PT, and
- d) Analysis of the primary endpoint of sustained remission at Week 52.

The population with and without trial impact (disruption) due to COVID-19 is defined in [Section 2.3.4](#).

In addition, upon meeting with Japan Health Authorities (PMDA) in April 2019, data for the components to calculate the PMR activity score (PMR-AS) were subsequently collected and the analysis plan is described in [Section 2.4.4.3](#).

2 STATISTICAL AND ANALYTICAL PROCEDURES

Data analyses will be performed in the double-blind (DB) 52-week treatment period and presented by two treatment groups (sarilumab 200 mg q2w with 14-week CS taper, and placebo with 52-week CS taper). Safety data will be summarized for the treatment and 6-week follow-up period.

2.1 ANALYSIS ENDPOINTS

2.1.1 Demographic and baseline characteristics

The baseline value is defined as the last available value prior to the first dose of study medication, SC IMP. For patients randomized but not treated, the baseline value is the last available value up to randomization. For PRO assessments, baseline value is defined as the last available value up to and including the day of administration of the first dose of SC IMP.

All baseline safety and efficacy parameters (apart from those listed below) are presented along with the on-treatment summary statistics in the efficacy and safety sections ([Section 2.4.4](#) and [Section 2.4.5](#)).

Demographic characteristics

The following demographic characteristics will be summarized separately by treatment and overall:

- Sex (Male, Female)
- Race (White, Black or African American, Asian, Native Hawaiian or Other Pacific Islander, American Indian or Alaska Native, Unknown, Not reported)
- Ethnicity (Hispanic or Latino, Not Hispanic or Latino, Unknown, Not reported)
- Region (Region 1 [Western countries], Region 2 [South America], and Region 3 [Rest of the World]); definitions of the regions are provided in [Section 2.5.7](#)
- Age (years)
- Age group (≥ 50 and < 65 , ≥ 65 and < 75 , ≥ 75 and < 85 , ≥ 85 years)
- Weight (kg)
- Weight group (< 60 , ≥ 60 and < 100 , ≥ 100 kg)
- Body mass index (BMI, kg/m^2)
- BMI group (< 25 , ≥ 25 and < 30 , ≥ 30 kg/m^2)
- Smoking status (never, former, current)
- Alcohol habits (never, occasional, monthly, weekly, daily)

Medical or surgical history

Medical or surgical history includes all the relevant findings within the lifetime of the patient.

This information will be coded to a “Lower Level Term (LLT)”, “Preferred Term (PT)”, “High Level Term (HLT)”, “High Level Group Term (HLGT)”, and associated primary “System Organ Class (SOC)” using the version of Medical Dictionary for Regulatory Activities (MedDRA) currently in effect at Sanofi at the time of database lock.

Disease characteristics at baseline

The following baseline disease characteristics as well as the other baseline characteristics will be summarized separately by treatment group:

- PMR signs and symptoms:
 - Morning stiffness (≤ 45 minutes, > 45 minutes)
 - Pain in the shoulders, neck and/or hip girdles
 - Limited range of motion of the shoulders and /or hip girdles (no upper limb elevation, elevation below the shoulder girdle, elevation up to the shoulder girdle, elevation above the shoulder girdle)
 - Constitutional symptoms (low grade fever, unintentional weight loss, fatigue, malaise, loss of appetite)
 - Other features judged by the investigator to be consistent with PMR disease activity
- Number of patients with prior PMR flares (≤ 6 months, 6 to 12 months or > 12 months prior to screening) and number of prior flares per patient
- Prednisone dose at baseline
- Highest dose and duration of corticosteroid taper taken for PMR from 24 weeks prior to screening up to baseline
- Physician global assessment of disease activity (MD-VAS)
- C-reactive protein (CRP) at baseline
- ESR at baseline
- Glucocorticoid toxicity at baseline*

*The baseline glucocorticoid toxicity is established by a composite index calculated from weighted scores assigned by toxicities. The scores are described in [Appendix J](#).

Any technical details related to computation, dates, and imputations for missing dates are described in [Section 2.5](#).

2.1.2 Prior or concomitant medications

All medications taken within a certain period of time before randomization and until the end of the study, including vaccines taken before screening, biological/non-biological disease modifying anti-rheumatic drugs [DMARDs] and immunosuppressive agents taken for patients with symptomatic PMR disease are to be reported in the case report form (CRF) pages. The highest dose and duration of all corticosteroids taper taken for PMR from 24 weeks prior to screening up to baseline and all corticosteroids taken during the study are also reported.

All medications will be coded using the World Health Organization – Drug Dictionary (WHO-DD) version currently in effect at Sanofi at the time of database lock.

- Prior medications are those the patient used prior to first investigational medicinal product (IMP) intake. Prior medications can be discontinued before first dosing or can be ongoing during treatment phase.
- Concomitant medications are any treatments received by the patient concomitantly to the IMP, during the treatment-emergent adverse event period ([Section 2.1.4](#)).

A given medication can be classified as a prior medication, as a concomitant medication, and/or as a post-treatment medication.

For patients who experience a disease flare and are in need of rescue therapy, study patients prescribed with rescue corticosteroids (non-investigational medicinal product) per investigator judgement during the course of the study will continue administration of subcutaneous (SC) IMP (sarilumab or its matching placebo) for the full duration of the 52-week treatment period.

Any technical details related to computation, dates, imputation for missing dates are described in [Section 2.5](#).

2.1.3 Efficacy endpoints

2.1.3.1 Primary efficacy endpoint(s)

The primary endpoint is the proportion of patients achieving sustained remission at Week 52, where the sustained remission at Week 52 is defined as having met all of the following parameters:

1. Achievement of disease remission not later than Week 12,
2. Absence of disease flare from Week 12 through Week 52,
3. Sustained reduction of CRP (to <10 mg/L, with an absence of successive elevations to ≥ 10 mg/L) from Week 12 through Week 52, and
4. Successful adherence to the prednisone taper from Week 12 through Week 52.

Components of primary endpoint are described as below:

1. Achievement of disease remission not later than Week 12

Disease remission is defined as resolution of signs and symptoms of PMR, and normalization of CRP (<10 mg/L). Note that a single CRP elevation (≥ 10 mg/L) is not considered absence of remission unless CRP remained elevated (≥ 10 mg/L) at the next study visit.

The status of normalization of CRP (<10 mg/L) will be determined based on the last two non-missing post-baseline CRP values measured up to Week 12. If at least one of them is <10 mg/L, then it is considered as normalization of CRP.

Signs and symptoms of disease

Evaluation of clinical signs and symptoms by the Efficacy Assessor at every study visit according to the schedule of assessment will include the following:

- Morning stiffness and/or pain, in the neck, shoulder and/or hip girdles
- Limited range of motion of the shoulders and/or hip girdles
- Constitutional symptoms, such as fatigue, weight loss and low-grade fever
- Other features judged by the clinician-investigator to be consistent with a PMR flare

The resolution of signs and symptoms of PMR is identified in eCRF “PMR Assessment” page with the question “Based upon the patient’s relevant medical history and the clinical assessment and responses provided above, does the patient have active PMR?” ticked as “No”. The resolution of signs and symptoms of PMR by Week 12 will be determined based on the last non-missing post-baseline PMR assessment measured up to Week 12.

Patients who took rescue CS due to active PMR prior to Week 12 or who permanently withdraw from the study treatment prior to Week 12 will be considered as not achieved disease remission by Week 12.

Note that during the initial 12 weeks of prednisone taper, treatment for one flare before Week 12 is permitted if it can be successfully treated with a low dose (≤ 5 mg/day) prednisone add-on taper regimen (completed prior to Week 12) and provided that all other sustained remission parameters are met.

2. Absence of disease flare from Week 12 through Week 52.

Flare is defined as either 1) recurrence of signs and symptoms attributable to active PMR plus an increase in CS dose due to PMR, or 2) elevation of ESR attributable to active PMR plus an increase in CS dose due to PMR. Increase in CS dose is defined as:

- Any dose increase during the protocol defined steroid taper, or
- Re-initiation of prednisone therapy after the protocol defined taper has been completed.

Patients with disease flare are identified as those with the reason for treatment ticked “rescue therapy” in eCRF “Steroid Medication” page and to the question “If Rescue Therapy, please specify” ticked either “Active PMR” or “Elevated ESR Attributable to Active PMR”.

3. Sustained reduction of CRP (to <10 mg/L, with an absence of successive elevations to ≥10 mg/L) from Week 12 through Week 52

The status of normalization of CRP from Week 12 through Week 52 will be determined based on the CRP values measured at Week 16, Week 20, Week 24, Week 32, Week 40 and Week 52. If there are two or more consecutive visits with CRP ≥10 mg/L, then it is categorized as no normalization of CRP. Intermittent missing CRP at Week 16, Week 20, Week 24, Week 32, Week 40 or Week 52 will be imputed using last value carried forward (LOCF) approach up to the last non-missing measurement.

4. Successful adherence to the prednisone taper from Week 12 through Week 52

Successful adherence to the prednisone taper from Week 12 through Week 52 is defined as patients who did not take rescue therapy from Week 12 through Week 52 and any excess prednisone (beyond the per protocol CS tapering regimen) with a cumulative dose of ≤100 mg (or equivalent), such as those employed to manage AE not related to PMR. The cumulative dose of excess prednisone use will be counted from baseline to Week 52 (does not include add-on prednisone taken prior to Week 12).

In addition, patients who permanently withdraw from the study treatment prior to Week 52 will be considered as not having achieved component 2, 3, or 4 for the primary endpoint.

Blinding of CRP and ESR assessment results

Investigators, including Efficacy Assessors, and patients will remain blinded to CRP and ESR results (except screening and baseline). Safety Assessors will also be blinded on post baseline CRP but will have access to ESR results.

ESR kits will be provided by the central laboratory while the test will be performed locally at site, results (the distance in millimeters (mm) that red blood cells has descended in 1 hour) will be blinded to Investigators including Efficacy Assessors and staff directly involved in efficacy assessment of study patients.

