### **8.1.3 Add on prednisone taper in the case of flare within initial 12 weeks**

During the initial 12 weeks of prednisone taper, treatment for one flare before Week 12 is permitted if it can be successfully treated with a low dose of prednisone ( $\leq 5$  mg/day) to add on to the CS tapering regimen provided that all other sustained remission parameters are met. The add-on prednisone must be completed by Week 12.

The prednisone for this add-on taper is provided in an open label manner consisting of 30 count blister (1 mg each) in a child resistant wallet. It is up to the investigator to decide on the CS dosage (with a maximum dose of ( $\leq 5$  mg/day) and taper schedule/duration according to the patient's disease status. The quantity of tablets to be taken daily will be written on the wallet and recorded in the eCRF. The patient will need to be monitored and in close communication with the site to ensure patients have taken the correct quantity of prednisone until the add-on taper is completed prior to Week 12.

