#### Signs and symptoms of PMR

Evaluation for clinical signs and symptoms by the Efficacy Assessor at every study visit according to the schedule of assessment should include, but are not limited to, the following:

- Morning stiffness and/or pain, in the neck, shoulder and/or hip girdles
- Limited range of motion of the shoulders and/or hip girdles
- Constitutional symptoms, such as fatigue, weight loss and low-grade fever
- Other features judged by the clinician-investigator to be consistent with a PMR flare

**Flare** is defined as either 1) recurrence of signs and symptoms attributable to active PMR plus an increase in CS dose due to PMR, or 2) elevation of ESR attributable to active PMR plus an increase in CS dose due to PMR.

Increase in CS dose is defined as:

- Any dose increase during the protocol-defined steroid taper
- Re-initiation of prednisone therapy after the protocol defined taper has been completed

*Note: During the initial 12 weeks of prednisone taper, treatment for one flare before Week 12 is permitted if it can be successfully treated with a low dose ( $\leq 5$  mg/day) prednisone add-on taper regimen (completed prior to Week 12) and provided that all other sustained remission parameters are met.*

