2.1.3.2 Secondary efficacy endpoint(s)

The following efficacy variables will be assessed:

- Components of sustained remission composite measure at Week 52
- Total cumulative corticosteroid (including prednisone) dose over during the treatment period
- Time to first PMR flare during the treatment period
- GTI Cumulative worsening score (CWS) and Aggregate improvement score (AIS) at Week 52.

Below are descriptions of these variables. Details related to imputation of GTI scores are described in [Section 2.5.2](#).

Components of sustained remission composite measure at Week 52

1. Proportion of patients who achieved disease remission by Week 12.
2. Proportion of patients who have no disease flare from Week 12 through Week 52.
3. Proportion of patients who have normalization of CRP (to <10 mg/L, with an absence of successive elevations to ≥ 10 mg/L) from Week 12 through Week 52.
4. Proportion of patients who successfully adhere to the prednisone taper from Week 12 through Week 52.

Total cumulative corticosteroid (including prednisone) dose during the treatment period

The total cumulative corticosteroid includes prednisone taper regimen per protocol, add-on prednisone prior to Week 12 or use of commercial prednisone during the study treatment period such as those employed to manage AE not related to PMR, and rescue corticosteroids dose prescribed for rescue therapy over the treatment period for PMR disease only.

Time to first PMR flare during the treatment period

The duration (in days) from randomization to first PMR flare after clinical remission and up to 52 weeks. Patients who never achieve remission will be censored at randomization day; and those who achieved clinical remission and never flared will be censored at the end of treatment assessment date up to Week 52.

The definition of PMR flare is provide in [Section 2.1.3.1](#) primary efficacy endpoint.

Clinical remission is defined as resolution of signs and symptoms and normalization of CRP (<10 mg/L). Intermittent missing CRP at visit will be imputed using last value carried forward (LOCF) approach. If missing signs and symptoms, then clinical remission is not achieved.

Glucocorticoid toxicity index (GTI) scores and components

The GTI is intended to capture glucocorticoid (GC)-related morbidity and GC-sparing ability of other therapies (2).

The GTI is composed of two components, the Composite GTI and the Specific List ([Table 2](#)).

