2.2 DISPOSITION OF PATIENTS

This section describes patient disposition for both patient status and the patient populations.

Screened patients are defined as all patients who signed the informed consent.

Randomized patients consist of all patients who signed informed consent with a treatment kit number allocated and recorded in the Interactive Voice Response System/Interactive Web Response System database, regardless of whether the treatment kit was used or not.

For patient status in the DB treatment period, the total number of patients for each one of the following categories will be presented in the clinical study report (CSR) using a summary table:

- Screened patients
- Screen failure patients and reasons for screen failure
- Non-randomized but treated patients
- Randomized patients
- Randomized but not treated patients
- Randomized and treated patients
- Patients who completed 52-week SC IMP study treatment period
- Patients who discontinued from 52-week study treatment period and the reasons for permanent SC IMP treatment discontinuation
- Patients who completed the study
- Patients who discontinued the study and the reasons for study discontinuation
- Patients who took CS rescue therapy
- Patients who took add-on prednisone
- Subject status at end of study visit

For all categories of patients (except for the screened and non-randomized categories) percentages will be calculated using the number of randomized patients as the denominator. Reasons for SC IMP treatment or study discontinuation, such as if it is related to COVID-19 will be presented in tables giving numbers and percentages by treatment group. Patient disposition by visit according to trial impact due to COVID-19 (visits that were delayed, not done, partially done on site, or partially done by phone, or not impacted) will also be provided.

A patient is considered as lost to follow-up at the end of the study if he/she is not assessed at the end of study visit.

All critical or major deviations potentially impacting efficacy analyses, randomization and drug dispensing irregularities and other major/critical deviations will be summarized in tables giving numbers and percentages of deviations by treatment groups. Critical or major deviations according to COVID19 impact will also be summarized.

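### Time to first flare finds flares only through the rescue-therapy tick, so post-remission flares before Week 12 treated with add-on prednisone alone are missed; the direction of any bias is not settled by the documents

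*SAP*

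**What the plan says.** **Definition.** SAP 2.1.3.1, component 2, defines a flare as returning PMR signs and symptoms, or a raised ESR attributed to PMR, together with a PMR-related increase in steroid dose. The increase can be "Any dose increase during the protocol defined steroid taper, or" a restart of prednisone once the taper is finished. Protocol 9.1.1 has the same limb: "Any dose increase during the protocol-defined steroid taper".

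**Data rule.** The SAP then says how flares are found: "Patients with disease flare are identified as those with the reason for treatment ticked" as rescue therapy on the Steroid Medication eCRF page, specified as active PMR or as elevated ESR attributable to it.

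**Time to first flare.** SAP 2.1.3.2 defines it as "The duration (in days) from randomization to first PMR flare after clinical remission and up to 52 weeks". It has no flare rule of its own: "The definition of PMR flare is provide in" Section 2.1.3.1. On censoring, "Patients who never achieve remission will be censored at randomization day"; remitters who never flare are censored at the end-of-treatment assessment, up to Week 52. SAP 2.4.4.2 plans Kaplan-Meier estimates and a Cox hazard ratio with confidence interval and p-value.

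**Add-on prednisone.** Protocol 8.1.3 states that "treatment for one flare before Week 12 is permitted if it can be successfully treated with a low dose of prednisone" of at most 5 mg/day, to be completed by Week 12. SAP 2.2 gives "Patients who took add-on prednisone" its own disposition row, separate from the row for steroid rescue.

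**The concern.** The data rule is narrower than the definition it is meant to implement. For the primary endpoint this does no harm: component 2 looks only from Week 12 onward, and one add-on-treated flare before then is expressly allowed. Time to first flare covers the weeks before Week 12, and neither document exempts add-on-treated flares from it.

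Take a patient who remits at Week 4, flares at Week 8, is settled with add-on prednisone and never needs rescue. The data rule treats this patient as flare-free and censors at end of treatment. If rescue comes later, the event is dated at the rescue, not at the first flare. The reported hazard ratio then describes time to first rescue-treated flare, under the label of time to first flare.

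**Working it through.** **1. Is add-on coded as rescue?** The eCRF page is not reproduced, so this has to be inferred. SAP 2.1.3.1, component 1, makes anyone who took rescue steroid for active PMR before Week 12 a non-remitter. The note that follows allows one add-on-treated flare before Week 12 without loss of response. If add-on were recorded as rescue for active PMR, the first rule would cancel the second. The documents also separate the two elsewhere:
- Protocol 8.1 (Table 1) lists add-on as an investigational product, while Protocol 8.2 makes rescue steroid non-investigational.
- SAP 2.1.3.2 names them as separate terms of cumulative steroid dose.
- SAP 2.2 gives them separate rows.

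Add-on is therefore not captured by the rescue tick.

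**2. Which flares are affected?** Only those that follow clinical remission, come before Week 12 and are treated with add-on alone. An add-on course started before remission is not an event on any reading of SAP 2.1.3.2.

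**3. Scheduled prednisone in the add-on window** (Protocol Appendix A; SAP Appendix B):
- Weeks 0–3, both groups: (15+15+14+12) × 7 = 392 mg.
- Weeks 4–11, Group 1: (10+9+8+7+6+5+4+3) × 7 = 364 mg.
- Weeks 4–11, Group 2: (12+12+10+10+9+9+9+9) × 7 = 560 mg.

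Group 1 tapers faster from Week 4, but on active sarilumab; Group 2 tapers more slowly on placebo injections.

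**4. Size.** The plan states no rate, hazard ratio or power for time to flare, and its power table concerns the primary endpoint only. The inputs here are therefore assumptions: later (rescue-treated) flares in 20% v 35%, sarilumab v placebo, and add-on flares, all after remission, at several rates. Let L = −ln(1 − later risk) and A = −ln(1 − add-on risk).

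Add-on flares omitted: L_S / L_P = 0.2231 / 0.4308 = 0.52, whatever the add-on rates.

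Add-on flares counted, with early and later flares independent, the ratio of cumulative hazards is (L_S + A_S) / (L_P + A_P). The Cox estimate differs somewhat because hazards are then not proportional; it was obtained by large simulation, with add-on flares spread over about Weeks 4–12 and later flares from Week 12 to Week 52.

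| Add-on flares, sarilumab v placebo | Cumulative-hazard ratio, counted | Cox HR, omitted → counted |
|---|---|---|
| 20% v 5% | (0.2231+0.2231)/(0.4308+0.0513) = 0.93 | about 0.52 → about 1.0 |
| 10% v 10% | (0.2231+0.1054)/(0.4308+0.1054) = 0.61 | about 0.52 → about 0.62 |
| 5% v 20% | (0.2231+0.0513)/(0.4308+0.2231) = 0.42 | about 0.52 → about 0.40 |

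If only half of the add-on flares follow remission, the 20% v 5% case becomes 10% v 2.5%: (0.2231+0.1054)/(0.4308+0.0253) = 0.72, with a Cox HR of about 0.8.

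**5. Direction.** From the formula, omission flatters sarilumab when A_S/A_P exceeds L_S/L_P and works against it when A_S/A_P is smaller. A second set of assumptions agrees. With later flares 40% v 40%, counting add-on flares leaves the HR at 1.00 if add-on rates are 10% v 10%, raises it to 1.24 if 20% v 10%, and lowers it to 0.72 if 5% v 20%.

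**The case against.** **The conceptual definition already covers add-on.** The tick-box sentence sits under component 2, Week 12 to Week 52, so it could be read as applying only there. That would make this an ambiguity about which text governs. But SAP 2.1.3.2 sends the reader to that section with no other data rule, and the tick is the only derivation a programmer is given.

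**The eCRF page is unseen.** True, but the conflict between the two pre-Week 12 rules in component 1 makes the inference strong.

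**The consequence is limited.** This stands. SAP 2.4.4.4 tests only cumulative steroid dose after the primary endpoint, so time to flare is not alpha-controlled. Add-on use is already visible in the disposition table and in cumulative dose. A patient who later needs rescue still counts, though late.

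**A stronger reading is tempting.** A reader might infer from the faster taper (3 v 9 mg/day at Week 11) that early flares fall mainly in the sarilumab arm, so that the rule favours sarilumab. The documents do not support this. They give no add-on rates by arm, doses are identical through Week 3, and active sarilumab pulls against the faster taper.

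**Conclusion.** The point holds as a mismatch between the SAP's flare definition and the rule used to find flares, confined to time to first flare. Under assumed later flares of 20% v 35%, counting the missed events moves the hazard ratio from about 0.52 to anywhere between about 0.40 and about 1.0 across the add-on rates tried. The shifts are smaller if only some add-on flares follow remission. Even at equal add-on rates, omission flatters sarilumab if sarilumab also reduces later flares; if placebo patients have clearly more add-on flares, it works against sarilumab. Bias is possible, and its sign is unknown.

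It would also go too far to say that every early flare should count, since the endpoint is limited to flares after clinical remission. The primary endpoint is unaffected. This should be corrected before analysis, but it does not threaten the trial's main conclusion.

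**What to change.** Add one sentence to SAP 2.1.3.2, for time to first flare only. The event is the first of (a) rescue steroid ticked as active PMR or as elevated ESR attributable to active PMR, or (b) an add-on prednisone course for a PMR flare before Week 12. In either case it counts only if it occurs after clinical remission, and it is dated at the start of that treatment. Leave component 2 of the primary endpoint as it is.

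Report the rescue-only Cox model as a sensitivity analysis, and show add-on use before Week 12 by arm so that readers can judge which way the difference runs.

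The cost is one sentence and one extra model. Protocol 8.1.3 already has daily add-on quantities entered in the eCRF, and SAP 2.1.2 has all on-study steroids reported. This assumes that start dates are among the recorded items, which should be confirmed against the form.
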